15.1.3 Injection Site Reaction Symptoms

Injection site reactions (ISRs) associated with single symptoms are recorded on the AE page (as a single symptom). ISRs with multiple symptoms are recorded as an AE of “Injection Site Reaction” on the AE page and the associated individual symptoms are recorded on the ISR symptom page.

In order to describe all ISR symptoms recorded, summaries will be based on the data collected on the ISR Symptoms page and also those single symptoms recorded as an adverse event.

Incidence and exposure-adjusted event rates of ISR Symptoms will be summarized by PT and separately by cohort and overall by treatment group using format as specified in [Table 5.4](#).

ISR Symptoms will be listed.

15.2 Clinical Laboratory Tests

Clinical laboratory tests (hematology, chemistry, and urinalysis) are performed at Screening, and pre-dose at Day 1, Day 8, Week 3, Week 6, Week 20, Week 39, Week 52 and early termination visit.

All summary tables will include laboratory assessments from baseline up to 30 days post treatment discontinuation. Results will be reported separately as hematology, chemistry, urinalysis, and “other laboratory tests”.

Laboratory tests will be graded as low/normal/high based on laboratory normal ranges. In addition, for laboratory tests with CTC grading available, all non-missing numeric results will be used to determine CTC grade programmatically, based on CTCAE v4.03.

For the following parameters, the distinction is made between significantly low/high results:

- Glucose (Hypoglycemia/Hyperglycemia)
- Hemoglobin (Anemia/Hemoglobin increased)
- Lymphocytes (Lymphocyte count decreased/Lymphocyte count increased)
- Potassium (Hypokalemia/Hyperkalemia)
- Sodium (Hyponatremia/Hyponatremia)
- Calcium (Hypocalcemia/Hypercalcemia)

The absolute values for pre-dose laboratory results at each scheduled visit, change from baseline in pre-dose laboratory results, and percent change from baseline in pre-dose laboratory results at each scheduled visit will be summarized and presented separately by cohort and overall by treatment group using format as specified in [Table 5.4](#).

Shift tables from baseline to worst post-baseline value (including scheduled and unscheduled visits) based on the CTC grading (Normal – Grade 5) will be generated for each Lab parameter where CTCAE grading is available, excluding parameters where CTCAE Grade does not rely on quantitative results alone (e.g. potassium and uric acid). Percentages are based on the number of subjects with each Baseline CTCAE grade (Normal, Grade 1, Grade 2, Grade 3, Grade 4, Grade 5, Missing, Overall). Shift tables will be produced separately by cohort and overall by treatment group using format as specified in [Table 5.4](#).

For laboratory tests where grades are not defined by CTCAE, or where CTCAE grading does not rely on quantitative results alone (e.g. potassium and uric acid), shift tables will be generated using the low/normal/high classification to compare to baseline to the worst post-baseline value.

Line plots of the mean results (+/- SD) for the pre-dose windowed absolute values including all scheduled visits will be provided for the following parameters by treatment group by cohort. Data from the sentinel subjects and randomized subjects received active treatment within each cohort will be pooled:

- Hematology: erythrocytes, hematocrit, hemoglobin, leukocytes, neutrophils, platelets, WBC and RBC count.
- Chemistry: alanine aminotransferase, albumin, alkaline phosphatase, aspartate aminotransferase, bicarbonate, bilirubin, blood urea nitrogen, calcium chloride, creatinine, direct bilirubin, glucose, lactate dehydrogenase, phosphate, potassium, protein, sodium, thyrotropin, vitamin D.

Listings:

In addition to the above tables, the following listings will be provided and will contain CTC grade and laboratory reference ranges:

- Hematology results
- Chemistry results
- Urinalysis results
- Urine chemistry results
- Other laboratory test results

- Laboratory results with CTCAE Grade ≥ 3

Listings will include all reported data and will be ordered by cohort, sentinel/randomized subject, subject ID, and assessment date.

15.3 Vital Signs

Vital Signs (heart rate, systolic/diastolic blood pressure, respiratory rate, and body temperature) are assessed at Screening, Day 1, Day 2, Day 3, Day 8, Week 3, Week 6, Week 13, Week 20, Week 26, Week 39, Week 52, safety follow-up visit, and early termination visit.

All summary tables will include vital signs recorded from baseline up to 30 days post treatment discontinuation.

The vital signs that are collected pre-dose and post-dose. Vital sign assessment frequency is shown below.

Table 15.3.1: Vital Sign Post-dose Assessment Frequency

Vital Sign Assessment Frequency				
Screening	After at least 5 min of rest, subject's vital signs are taken, preferably in sitting or supine position. Vital sign measurements should be repeated and documented 3 times with at least 5 min intervals between assessments.			
	Assessment Frequency			
Dosing Visits	0-1 hr post-dose	0-2 hr post-dose	2-4 hr post-dose	4-8 hr post-dose
Days 1, 2		q 15 min (± 5 min)	q 30 min (± 5 min)	q 60 min (± 10 min)
Days 3, 8		q 15 min (± 5 min)	q 30 min (± 5 min)	
Subsequent dosing visits	q 15 min (± 5 min); final assessment prior to end of visit (if longer than 1 hr)			

The absolute values for pre-dose vital signs at each scheduled visit, and change from baseline in pre-dose vital signs at each scheduled visit will be summarized and presented separately by cohort and overall by treatment group using format as specified in [Table 5.4](#).

Line plots will be generated, which present the mean pre-dose and post-dose absolute values (+/-SD) for each visit by treatment group by cohort. Data from the sentinel subjects and randomized subjects received active treatment within each cohort will be pooled.

The percentage of subjects experiencing at least one instance of a decrease of 20% in diastolic blood pressure from pre-dose to same-day post dose will be summarized by visit and for overall (each subject meeting criteria at any time in the study will be counted only once) for both sentinel subjects and randomized subjects.

Shift tables (Diastolic BP <40mmHg, Diastolic BP \geq 40mmHg) from pre-dose to lowest same-day post-dose value category (Diastolic BP <40mmHg, Diastolic BP \geq 40mmHg) will

be generated by visit and for overall (each subject meeting criteria at any time in the study will be counted only once) for both sentinel subjects and randomized subjects.

Shift tables (Diastolic BP <30mmHg, Diastolic BP \geq 30mmHg) from pre-dose to same-day lowest post-dose value category (Diastolic BP <30mmHg, Diastolic BP \geq 30mmHg) will be generated by visit and for overall (each subject meeting criteria at any time in the study will be counted only once) for both sentinel subjects and randomized subjects.

Shift tables (Systolic BP < (70mmHg plus 2 x Age), Systolic BP \geq (70mmHg plus 2 x Age)) from pre-dose to lowest same-day post-dose value category ((Systolic BP < (70mmHg plus 2 x Age), Systolic BP \geq (70mmHg plus 2 x Age))) will be generated by visit and for overall (each subject meeting criteria at any time in the study will be counted only once). Subject's age used in this calculation is the integer value.

A listing of vital sign data will also be provided.

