4.4 Study Dosage and Administration

In Study 111-206, sentinel subjects in Cohort 1 will receive an initial daily dose of 15 µg/kg. All available safety and PK data will be reviewed after 3 sentinel subjects reach Day 8. If the criteria for dose adjustment are met, the 3 sentinel subjects will be started on the new adjusted dose at their next scheduled visit and the remainder of the subjects in the age cohort will also be enrolled starting at the new adjusted dose. The 3 sentinel subjects for the second and third cohorts will be evaluated similarly to the sentinel subjects in the first cohort for potential dose adjustment. Additional sentinels may be added to any cohort if needed for additional safety and/or PK assessment.

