4.5 Sample Size Determination

Approximately 70 subjects aged 0 to < 60 months at study entry will participate in 111-206. No formal sample size calculations were performed. The number of subjects is considered appropriate to evaluate the safety and efficacy of vosoritide in the target population.

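### By-visit blood pressure tables count the worst reading of the day, but readings per visit drop from about 16 to 4 or 5 after Day 8, so incidence can fall with the schedule alone

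*SAP*

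**What the plan says.** Section 15.3 (SAP Version 2.0) plans four blood pressure tables that compare pre-dose with post-dose values on the same day. The first reports "The percentage of subjects experiencing at least one instance of a decrease of 20% in" diastolic pressure, so one qualifying reading is enough; the same sentence continues that this fall in "diastolic blood pressure from pre-dose to same-day post dose will be summarized by visit and for overall". The other three are shift tables for diastolic pressure below 40 mmHg, diastolic pressure below 30 mmHg, and systolic pressure below an age-based limit. They go "from pre-dose to lowest same-day post-dose value category" or, in the 30 mmHg table, "from pre-dose to same-day lowest post-dose value category". All four are given by visit as well as overall. Section 24 records that the by-visit presentation was added in Version 2.0.

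Table 15.3.1 sets the reading schedule. Days 1 and 2 have readings every 15 minutes to 2 hours, every 30 minutes to 4 hours and hourly to 8 hours. Days 3 and 8 stop at 4 hours. Later dosing visits have "q 15 min (± 5 min); final assessment prior to end of visit (if longer than 1 hr"). Section 15.3 sets no common post-dose window for the four tables and makes no allowance for the number of readings.

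On dose, Section 4.2 says the Cohort 2 sentinels began at 15 µg/kg and were escalated to 30 µg/kg after review of PK data. Section 4.4 places the review after three sentinels reach Day 8. If the criteria for adjustment are met, "the 3 sentinel subjects will be started on the new adjusted dose at their next scheduled visit". In the visit list of Section 15.3, the first visit after Day 8 is Week 3.

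**The concern.** An any-reading rule and a lowest-of-the-day rule both depend on how often one looks. With the same child, dose and true risk, sixteen readings will find a fall more often than four. A by-visit table invites the reader to follow a column down from Day 1 to Week 52, and here the number of readings drops at Day 3 and drops sharply after Day 8. A decline at that point could be read as adaptation to the drug when it may be only fewer measurements.

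The Cohort 2 sentinels are a special case. Their starting dose was observed on the dense schedule. Under Section 4.4 and Table 15.3.1 taken together, the escalated dose falls on the sparse one. Anyone comparing early with late visits in that column would be comparing unequal chances of detection, and the higher dose can look safer than it is.

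**Working it through.** The SAP gives no expected incidence to reproduce. Section 4.5 states "No formal sample size calculations were performed", and these tables are descriptive. The check is how far the reading schedule alone moves the by-visit percentages.

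**Readings per visit (Table 15.3.1, window length divided by interval)**
- Days 1 and 2: 120/15 + 120/30 + 240/60 = 8 + 4 + 4 = 16
- Days 3 and 8: 8 + 4 = 12
- Later dosing visits: 60/15 = 4, or 5 with the final reading

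**Chance that a child is flagged.** Let p be the chance that one reading qualifies. The documents do not give p, so 1% to 10% is an assumption, held the same at every visit. With independent readings, P(flagged) = 1 − (1 − p)^k.

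| p | k = 16 | k = 12 | k = 5 | k = 4 | ratio 16 to 4 |
|---|---|---|---|---|---|
| 1% | 14.9% | 11.4% | 4.9% | 3.9% | 3.8 |
| 2% | 27.6% | 21.5% | 9.6% | 7.8% | 3.6 |
| 5% | 56.0% | 46.0% | 22.6% | 18.5% | 3.0 |
| 10% | 81.5% | 71.8% | 41.0% | 34.4% | 2.4 |

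**Correlated readings.** Readings within a day are not independent. With an exchangeable Gaussian correlation and p = 5%:

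| correlation | k = 16 | k = 12 | k = 5 | k = 4 | ratio 16 to 4 |
|---|---|---|---|---|---|
| 0.3 | 39.9% | 34.2% | 19.3% | 16.4% | 2.4 |
| 0.5 | 30.9% | 27.0% | 16.6% | 14.4% | 2.1 |
| 0.8 | 17.8% | 16.2% | 11.7% | 10.6% | 1.7 |

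Over p from 2% to 10% and correlation from 0.3 to 0.8, the ratio runs from 2.9 down to 1.5.

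**Lowest value.** For independent normal readings, the expected minimum lies 1.77 SD below the mean with 16 readings and 1.03 SD below with 4. The lowest value is thus 0.74 SD deeper on Days 1 and 2 by count alone, which feeds the three shift tables.

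**A dose step with a true effect.** Suppose the drug effect is confined to the first hour and its per-reading risk doubles on escalation, with a 2% background afterwards.
- From 3% to 6%: Day 1 gives 1 − 0.97^4 × 0.98^12 = 30.5%; the first escalated visit gives 1 − 0.94^4 = 21.9%. A fifth reading at background risk makes the latter 1 − 0.94^4 × 0.98 = 23.5%. The increase appears as a decrease.
- From 6% to 12%: 38.7% against 1 − 0.88^4 = 40.0%. The increase almost disappears but does not reverse.

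**After restricting to 0-1 hour.** Every dosing visit then contributes 4 scheduled readings. At a constant 5%, Day 1 and Week 3 both give 18.5%. In the two dose-step cases the first-hour figures are 11.5% against 21.9% and 21.9% against 40.0%, so the true increase is visible.

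**The case against.** A reader might infer that the plan will make the escalated dose look safer than the starting dose. The documents do not support that as a certainty or as a planned comparison.
- Section 15.3 does not split these tables by dose; the 15 versus 30 µg/kg split is specified only for compliance and exposure (Sections 12 and 13).
- Within-subject escalation is documented only for the Cohort 2 sentinels, three planned. With three children the column can show only 0, 33, 67 or 100%.
- Randomized Cohort 2 subjects and all of Cohort 3 received 30 µg/kg while under 24 months, so 30 µg/kg is also observed on the dense early schedule.
- The second dose-step case above shows that the escalated dose need not look safer.

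A reader might also infer that Sections 4.2 and 4.4 contradict Table 15.3.1. They do not. They are compatible, the visit at which escalation took place is not stated, and any extra monitoring at a dose change may sit in the protocol, which is not shown.

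Other points also have weight. Both randomized arms share one schedule, so vosoritide versus placebo at the same visit is fair. The Table 5.4 layout puts the cohort's placebo column in the same table, where a schedule-driven drop would also appear. Many later visits probably exceed an hour, because Section 18 plans urine about 2-4 hours after dosing where possible and PK samples to 120 minutes; the count is then 5 rather than 4. Hypotension is also reported through adverse events (Section 15.1.2), mean pre- and post-dose plots and listings, none of which uses a worst-reading rule.

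All of this limits the reach of the point. It does not make a column comparable with itself across Day 8, and the placebo column serves as a check only for a reader who knows to look there.

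**Conclusion.** The point stands as a cheap improvement to descriptive safety output. In every column of the four by-visit tables, incidence on Days 1 to 8 and incidence from Week 3 onward rest on different numbers of readings, so a decline between them could arise from the schedule alone. At an assumed 5% per reading with independence, the expected figures are 56%, 46% and 19-23%. With plausible correlation the 16-versus-4 ratio is about 1.5 to 2.9. The direction follows from the SAP's own schedule and rules; the size rests on assumed per-reading risks.

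Same-visit comparison of the randomized arms is unaffected, and comparisons among visits from Week 3 onward are close to like-for-like (4 or 5 readings). For the Cohort 2 sentinels, an early-versus-late reading can make the higher dose look safer than it is; it does not have to. No judgement on dose or on the monitoring schedule follows from this.

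**What to change.** In Section 15.3, repeat the four by-visit tables (20% diastolic fall; diastolic below 40 mmHg; diastolic below 30 mmHg; age-based systolic limit) using only the 0-1 hour post-dose readings common to every dosing visit. Select them by nominal time, so that the ±5 minute allowance does not drop the 60-minute reading. Keep the all-readings tables alongside, with a footnote giving the scheduled number of readings for each visit.

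The SAP already does something similar for ECGs: Section 15.5 repeats those summaries on readings 20-40 minutes after dosing, around the expected peak concentration. That interval lies inside the shared first hour, so the restricted blood pressure tables keep the expected peak.

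The cost is one filter on data already collected and one extra set of tables. Falls after the first hour appear only in the all-readings version, which is why both are needed.

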15.4 Biological Parental Standing Height

If available standing height of the subject's biological parents will be listed.

15.5 Electrocardiogram

Electrocardiogram (ECG) data are recorded at Screening, Day 1, Day 8, Week 6, Week 13, Week 20, Week 26, Week 39, Week 52, safety follow-up visit, and early termination visit.

ECG assessments are performed in triplicate on Day 1 (pre-dose and post-dose) and on study day visits (post-dose only).

Summaries will be provided over all planned assessments, and repeated with the requirement that all post-dose ECG assessments should occur around the expected time of C_{Max}, i.e., 20-40 minutes post-dose. The mean results of the ECG assessments meeting these criteria will be used for summaries and analyses.

All measures and means of the measures will be included in the listings.

The following ECG results will be summarized and presented separately by cohort and overall by treatment group using format as specified in [Table 5.4](#) at scheduled visits:

- ECG Mean Heart Rate (beats/min)
- QT interval (msec)
- QTcF interval (msec)
- PR interval (msec)

- RR interval (msec)
- QRS Duration (msec)

The following endpoints will be summarized at scheduled visits, and across all time points (using the highest mean QTc value), and presented by cohort and overall by treatment group using format as specified in [Table 5.4](#).

- Percentage of subjects with QTcF >450 to ≤480ms, >480 to ≤500ms, >500 msec

The following endpoints will be summarized at scheduled visits, and across all time points, and presented by cohort and overall by treatment group using format as specified in [Table 5.4](#)

- Percentage of subjects experiencing at least one instance of a (decrease in mean heart rate from pre-dose baseline >25% and a mean heart rate <50 beats/min) post-dose.
- Percentage of subjects experiencing at least one instance of an (increase in mean heart rate from pre-dose baseline >25% and a mean heart rate >100 beats/min) post-dose.

The following endpoints will be summarized across all time points and presented by cohort and overall by treatment group using format as specified in [Table 5.4](#).

- Percentage of subjects with a QTcF increase of 60ms from pre-dose baseline at any time
- Percentage of subjects with QTcF changes from pre-dose baseline of >30 and ≤ 60 msec, or >60 msec at any time

Listings will be provided and ordered by cohort, sentinel/randomized subject, treatment group, and visit:

- All ECG results.
- All ECG results for subjects with a QTc increase of 60msec from pre-dose baseline.

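### The overall QTcF category table has no post-dose limit and no baseline reference, so the Day 1 pre-dose ECG can set a child's category (minor correction to a descriptive safety table)

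*SAP*

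**What the plan says.** All ECG outputs at issue are in SAP Section 15.5, which reads the same in versions 1.1 and 2.0.

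- **Output.** "Percentage of subjects with QTcF >450 to ≤480ms, >480 to ≤500ms, >500 msec". These are absolute categories, presented by cohort and overall by treatment group.
- **Value used.** The categories are "summarized at scheduled visits, and across all time points (using the highest mean QTc value").
- **ECGs taken.** "ECG assessments are performed in triplicate on Day 1 (pre-dose and post-dose) and on study day visits (post-dose only"). The Day 1 pre-dose triplicate is therefore a planned assessment.
- **Scope.** "Summaries will be provided over all planned assessments, and repeated with the requirement that all post-dose ECG assessments should occur around the expected time" (Cmax). The timing condition in the repeat applies to the post-dose ECGs only.

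Section 5 keeps the screening visit out of descriptive summaries over time, although screening data may supply the baseline. It does not exclude the Day 1 pre-dose ECG.

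**The concern.** A table of QTcF categories by treatment group is normally read as what happened on treatment. A maximum over all time points, taken as written, also admits a value recorded before the first injection. Two kinds of children then enter the count without having newly crossed a threshold:

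- those above 450 msec only before dosing;
- those above 450 msec both before and after dosing.

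Counts unrelated to treatment would be added to every column: sentinel, randomized vosoritide, randomized placebo and all vosoritide treated. Between the randomized arms this dilutes a real difference. Because the arms are small, it can also produce a chance imbalance. Safety and tolerability is a primary objective of the study (Section 4.1), so the table should show what it appears to show.

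**Working it through.** **1. Wording compared across the SAP's outlier and shift tables**

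| Output | Section | Limit or reference stated |
|---|---|---|
| Heart-rate decrease | 15.5 | "decrease in mean heart rate from pre-dose baseline >25% and a mean heart rate <50 beats/min) post-dose" |
| Heart-rate increase | 15.5 | change from pre-dose baseline, "and a mean heart rate >100 beats/min) post-dose" |
| QTcF change >30 to ≤60, >60 msec | 15.5 | change from pre-dose baseline |
| Laboratory shifts | 15.2 | "Shift tables from baseline to worst post-baseline value (including scheduled and unscheduled visits) based on the CTC grading" |
| Blood pressure shifts | 15.3 | pre-dose to lowest same-day post-dose category |
| Absolute QTcF categories | 15.5 | none |

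Only the last row has neither a post-dose limit nor a baseline reference.

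**2. Whether the other QTcF tables separate new from pre-existing prolongation**

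Take one child at 445 msec pre-dose and 460 post-dose, and another at 460 pre-dose and 455 post-dose. The changes are 460 − 445 = +15 and 455 − 460 = −5, so neither child reaches the >30 msec change category. The highest value is 460 for both, so both fall in >450 to ≤480. The first crossing is new and the second is not, and no planned summary table tells them apart.

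**3. Arm sizes**

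Section 4.2 gives minimum randomized numbers of 27, 17 and 17. The sum is 61, and 61/2 is about 30 per arm overall. Cohort arms are 17/2 to 27/2, about 8 to 14 children, so one child is 1/14 = 7% to 1/8 = 12.5% of a cohort arm.

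**4. Chance that an arm contains a child above 450 msec before treatment**

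The SAP gives no figure for the prevalence p, so a range is assumed. For an arm of 30 the chance is 1 − (1 − p)^30:

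| Assumed p | Chance of at least one | Expected children (30p) |
|---|---|---|
| 1% | 26.0% | 0.3 |
| 2% | 45.5% | 0.6 |
| 5% | 78.5% | 1.5 |
| 10% | 95.8% | 3.0 |

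**5. How much the literal maximum changes the count**

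The SAP states no figure to reproduce, so this is illustrative. Each child has 1 pre-dose value and 8 post-dose values (Day 1, Day 8, Weeks 6, 13, 20, 26, 39, 52), with no drug effect. Assumed: normal values, SD 20 msec, mean 400 to 420 msec, within-child correlation 0.3 to 0.7; 400,000 simulated children per row. Entries are percentages of children.

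| Correlation | Mean | Any time >450 | Post-dose >450 | Pre-dose only | Post-dose >450 and pre-dose ≤450 |
|---|---|---|---|---|---|
| 0.3 | 400 | 4.8 | 4.3 | 0.47 | 4.2 |
| 0.3 | 410 | 15.3 | 14.1 | 1.28 | 13.1 |
| 0.3 | 420 | 35.7 | 33.3 | 2.38 | 29.0 |
| 0.5 | 400 | 4.1 | 3.8 | 0.36 | 3.5 |
| 0.5 | 410 | 12.5 | 11.5 | 0.92 | 10.2 |
| 0.5 | 420 | 29.0 | 27.4 | 1.66 | 22.3 |
| 0.7 | 400 | 3.1 | 2.9 | 0.21 | 2.5 |
| 0.7 | 410 | 9.4 | 8.8 | 0.56 | 7.1 |
| 0.7 | 420 | 22.2 | 21.2 | 1.04 | 15.5 |

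The pre-dose-only group is 0.21 to 2.38 percentage points of an arm. In an arm of 30 that is 0.0021 × 30 = 0.06 to 0.0238 × 30 = 0.71 children. As a share of all flagged children it runs from 1.04/22.2 = 4.7% to 0.47/4.8 = 9.8%. A second assumed grid (mean 400 to 425, between-child SD 12 to 18, within-child SD 8 to 12 msec) gives about 3 to 10%.

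Children above 450 msec both before and after dosing are the post-dose column minus the last column: 4.3 − 4.2 = 0.1 up to 21.2 − 15.5 = 5.7 percentage points. A post-dose limit alone would leave them in the count.

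**The case against.** The strongest reply is that the SAP never defines time points. Section 15.5 uses the same phrase for the heart-rate and QTcF-change outliers, where only assessments after baseline can be meant, so a programmer could reasonably read it that way here too. That reading is open, but for those outputs the limit comes from the bullets themselves, and no text supplies one for the absolute categories.

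The second reply is that other outputs protect the reader. The same categories are given at scheduled visits, changes from pre-dose baseline are tabulated, and every ECG result is listed. With about 30 children per randomized arm, a flagged child can be traced. This stands as partial mitigation. The by-visit rows do not link a visit to the child's baseline category, and the SAP does not say how a Day 1 row combines pre-dose and post-dose ECGs. A listing is not a pre-specified summary.

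The third reply is that the table is descriptive, with no test or decision rule, and that QT prolongation is not among the events of interest in Section 15.1.2. This is correct and limits the weight of the point.

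A reader might also infer that every flagged child with a pre-dose value above 450 msec, about 13 to 42% of flagged children on the second assumed grid, is there because of this wording. That does not follow. Most of them are also above 450 msec after dosing and would be counted under a post-dose maximum too.

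**Conclusion.** The point holds as a minor correction. As written, the rule allows a value recorded before the first injection to set a child's overall QTcF category, and the table does not separate pre-existing from new prolongation. Under the assumed distributions, about 0.2 to 2.4 percentage points of an arm are flagged by the pre-dose value alone. These figures rest entirely on assumed means, SDs and correlations.

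Two stronger readings are not supported. One is that the table biases the comparison of vosoritide with placebo: the randomized arms are affected alike in expectation, which leaves dilution and chance imbalance. The other is that this is the principal repolarization output: the SAP does not rank it above the change-from-baseline tables. The efficacy analyses are not touched.

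**What to change.** In Section 15.5, define the across-time category on each child's highest post-dose, on-treatment mean QTcF. Present it as a shift from the Day 1 pre-dose category (≤450, >450 to ≤480, >480 to ≤500, >500 msec), following the pattern the SAP already uses for laboratory values and blood pressure. The post-dose limit removes the pre-dose-only children, and the cross-tabulation separates those who were already above a threshold.

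The cost is one sentence and one table shell. All values are already collected.
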